5.6 Schedule of assessment in diagrammatic format

Event/Visit	Screening	Pre-op 72 hrs before surgery	Pre-op ≥ 48 hrs before surgery	Day of surgery	Postop day 1 ± 6 hrs	Postop day 2 ± 6 hrs	Postop day 3 ± 6 hrs (if subject was not discharged on postop day 2)	30 days after surgery
Inclusion/exclusion criteria	x							
Informed consent	x							
Demographic information	х							
Medical history	x							
Prior and concomitant medications	x			х	х	х	х	х
Height and weight				Х				
EQ-5D-3L	x							х
Planned level of care	х							
Level of care				Х	Х	Х	х	
Randomisation		Х						
Perioperative information				х				
Review of medical notes	х		х		х	х	х	х
Restart drug						Х		
Blood sample			X*	Х	Х	Х		
Hemoglobin †	x†							
Creatinine †	x†			Х	х	х	x	
Blood pressure/ heart rates				x	x	x		
Intravenous fluids				Х	х	х	х	х
Telephone contact			Х					х
Review of AE/SAE				Х	х	х	х	
End of trial form								х

^{*} provided patient is in hospital.

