2 TRIAL OBJECTIVES AND DESIGN

2.1 Trial objectives

Primary objective – To determine whether continuing perioperative ACE-I and/or ARB reduces the risk of myocardial injury, identified using high-sensitivity plasma troponin measurement during the first 48 hours after surgery.

Secondary objective – To determine whether continuing perioperative ACE-I and/or ARB reduces the risk of postoperative morbidity.

Tertiary objective – To determine whether continuing perioperative ACE-I and/or ARB results in changes to perioperative heart rate, blood pressure or immune function.

Primary outcome measure

The primary outcome is myocardial injury, a binary variable based on plasma high sensitivity Troponin-T) measured in blood samples collected immediately before the induction of anaesthesia, and then postoperative day 1 ± 6 hours and day 2 ± 6 hours after surgery. The primary outcome is met under the following conditions:

- Troponin-T ≥15 ng/L within 48 hours after surgery with a pre-operative value <15 ng/L

 OR
- Troponin-T increase ≥5 ng/L within 48 hours after surgery with a pre-operative value ≥15ng/L

Secondary outcome measures

- 1. Highest level of Troponin-T measured within 48 hours of surgery (continuous variable)
- 2. Infection within 30 days of surgery*
- 3. Myocardial infarction within 30 days of surgery*
- 4. Acute heart failure within 30 days of surgery*
- 5. Stroke within 30 days of surgery*

Tertiary outcome measures

Changes in heart rate, blood pressure and tests of immune function.

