5.3 Randomisation procedures

Once a medically qualified member of the research team has confirmed the patient's eligibility, the process of randomisation can commence. Randomisation will occur after the participant has provided informed consent, but 72 hours before the surgical procedure is due to start. Participants will be centrally allocated to a treatment group in a 1:1 ratio using a computer generated dynamic procedure (minimisation) with a random component.

Minimisation variables are trial centre, surgical procedure category (surgery involving the gut AND all other surgery) and ACE-I/ARB category (ACE-I or ARB). Each participant will be allocated with 80% probability to the treatment group that minimises between group differences in these factors among all participants recruited to the trial to date, and to the alternative group with 20% probability. The allocation sequence is generated by an automated algorithm and is concealed to all trial investigators. The system for generating the allocation sequence is bespoke and was developed in–house; it has been validated for use by the trial statistician, [name], Queen Mary University of London.

To enter a patient into the SPACE trial, research staff at the site will log on to a secure web-based randomisation and data entry platform hosted by Queen Mary University of London and complete the patient's details to obtain a unique patient identification number and treatment group allocation. Patients will receive a patient advice letter confirming their treatment group allocation. In addition, patients will be told in person or by telephone, together with a reminder(s) via text message before hospital admission. Research staff will document randomisation allocation on the CRF. Once the patient has been successfully allocated to a treatment group, this will be documented in the enrolment log.

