5.5 Schedule of treatment for each visit

The trial intervention period will commence 72 hours prior to day of surgery and continue for at least 48 hours after surgery. After randomisation, participants will receive a patient advice letter confirming their treatment group allocation, to stopping or continuing their ACE-I and/or ARB. Participants will also be reminded by telephone call and/or text message, or in person if they are in hospital. If the patients are not in hospital, they will receive a telephone call and/or text message or visit the day before surgery. ACE-I and/or ARB will be continued or discontinued as per treatment group allocation and this will continue until 48 hours after the end of surgery. Since ACE-I and ARB have differing durations of action, participants will receive drug-specific instructions as to when to stop. When the ACE-I and/or ARB duration of action is equal to, or more than, 24 hours, the drug will be stopped 48 hours prior to surgery. All other ACE-I and/or ARB will be stopped on the day before surgery (see appendix for specific drugs' half-life and duration of action).

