5.7 Follow-up procedures

Participants will be followed up on days 1, 2, and 3 (if the patient remains in hospital) after surgery. The end of the study is defined as the point when the last patient has completed 30-day follow-up. The follow-up will be completed over the telephone and therefore the paper CRF will be the source data for any patient-reported outcomes during this period. To minimise bias, follow-up data will be collected by a study team member who is blinded to the treatment group allocation. Similarly, investigators will review a participant's medical record (paper or

[†] within 4 weeks prior to surgery

s At some centres heart rate may be measured with a Holter monitor and blood pressure cuff to collect ambulatory blood pressure (ABP) and in other sites the data will be obtained from the clinical notes. The Holter monitor and BP cuff will be loaned to the site by the Sponsor.

electronic) after surgery, unaware of the primary outcome result (which is measured after the end of the trial).

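### Blood pressure and heart rate are first scheduled on the day of surgery, after randomisation and stopping, so the tertiary outcome of change in them has no scheduled pre-randomisation reference.

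*Protocol*

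**What the plan says.** **Outcome.** The tertiary objective in section 2.1 asks whether continuing the drugs "results in changes to perioperative heart rate, blood pressure or immune function". The tertiary outcome is listed as "Changes in heart rate, blood pressure and tests of immune function". Neither sentence names a reference time.

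**Schedule.** In section 5.6 the row "Blood pressure/ heart rates" has marks under day of surgery, postoperative day 1 and postoperative day 2. The screening column and both preoperative columns (72 hours, and 48 hours or more, before surgery) are blank. A review of medical notes is scheduled at screening. Haemoglobin and creatinine have a screening value, which a footnote allows to date from up to 4 weeks before surgery.

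**Timing of allocation and stopping.** Section 5.3 places randomisation after consent "but 72 hours before the surgical procedure is due to start". Section 5.5 says: "The trial intervention period will commence 72 hours prior to day of surgery". For longer-acting agents "the drug will be stopped 48 hours prior to surgery". For the rest: "All other ACE-I and/or ARB will be stopped on the day before surgery". Appendix 1 lists intervals of 1, 2 or 5 days, none shorter than one day.

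**Source of the readings.** A footnote to the schedule (it runs into section 5.7 in the text) says: "At some centres heart rate may be measured with a Holter monitor and blood pressure cuff to collect ambulatory blood pressure". At other sites the values come from the clinical notes. Trial centre is a minimisation variable (section 5.3).

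**The concern.** An outcome described as a change needs a starting point. In a randomised comparison that starting point should precede allocation, or at least precede any difference in treatment. Here the earliest scheduled blood pressure and heart rate follow both randomisation and, in the stop arm, withdrawal of drugs prescribed to lower blood pressure. If that reading becomes the baseline, whatever allocation has already done to it is removed from the estimate. If it is not used, no scheduled value is left for adjustment. An analysis plan can define the contrast, but it cannot supply a reading that nobody was asked to record.

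A second, smaller matter is that the source varies by site. Ambulatory devices and clinical notes do not give the same quantity, so pooled values carry between-centre differences in method.

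**Working it through.** **1. Order of events in the stop arm**, from sections 5.3, 5.5, 5.6 and Appendix 1:

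| Time | Event | Blood pressure and heart rate scheduled? |
|---|---|---|
| Screening | Consent, history, notes review | No |
| 72 h before surgery | Randomisation | No |
| 48 h before surgery, or the day before, by drug (section 5.5) | Drug stopped | No |
| Day of surgery | Surgery | Yes (first reading) |
| Days 1 and 2 | Follow-up | Yes |

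The first reading follows allocation in both arms and follows stopping throughout the stop arm. No other section schedules an earlier one.

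**2. What a change from the day-of-surgery value estimates.** Let D0 be the difference between arms (stop minus continue) on the day of surgery and D2 the difference on day 2. The difference in mean change is D2 − D0. The documents give no blood pressure effect, standard deviation or correlation, so these figures (mmHg systolic) are assumptions:

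| D0 | D2 | Change contrast D2 − D0 |
|---|---|---|
| 8 | 10 | 10 − 8 = 2 |
| 8 | 4 | 4 − 8 = −4 |
| 8 | 0 | 0 − 8 = −8 |

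With f = D0/D2, the share of the day 2 effect retained is 1 − f: 75%, 50%, 25% and 0% for f = 0.25, 0.5, 0.75 and 1. Above f = 1 the sign reverses. If D0 and D2 have opposite signs, f is negative and the contrast is exaggerated. The direction of the distortion therefore cannot be stated in advance.

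Using the day-of-surgery value as a covariate does not avoid this. With within-arm slope b, the adjusted difference is D2 − b × D0. For an assumed b = 0.5 in the first row it is 10 − 0.5 × 8 = 6, not 10.

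**3. What remains without a baseline.** The difference in mean level on day 2 estimates D2 itself and is unbiased under randomisation. The loss is one of precision. If a pre-randomisation value correlates r with the later value, adjusting for it multiplies the residual variance by 1 − r²:

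| Assumed r | 1 − r² | Reduction in variance |
|---|---|---|
| 0.3 | 0.91 | 9% |
| 0.5 | 0.75 | 25% |
| 0.7 | 0.51 | 49% |

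A plain change score from a true baseline, with equal variances, has relative variance 2(1 − r): 1.4, 1.0 and 0.6 for the same r. Adjustment is better than a change score at each of these values.

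**4. Sample size, to confirm it is untouched.** Section 9.2 uses 50% versus 30%, 90% power, 5% type I error (taken as two-sided) and 5% loss. The usual two-proportion formula without continuity correction gives 124 per arm; 124/0.95 = 130.5, so 131 per arm and 262 in total, against 260 stated. Power with 130 × 0.95 per arm is 0.899. Nothing in this calculation involves blood pressure or heart rate.

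**The case against.** The strongest reply is that the protocol never says change from the day-of-surgery value will be analysed. The objective can be read as asking whether allocation alters perioperative values. A comparison of levels answers that without a baseline, and choosing the contrast is ordinary analysis-plan business. This stands as far as it goes: the distortion in step 2 is conditional on that reference being used. It does not explain why the outcome is worded as a change when the only early value on schedule is post-treatment.

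It can also be said that notes are reviewed at screening, so an earlier reading may be retrievable. That is fair, and it is why the remedy is cheap. But the schedule does not ask for the value to be recorded.

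Three stronger readings are tempting, and the documents do not support them:

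- **Bias toward no difference.** A reader might infer this, but step 2 shows that the direction depends on effects the documents do not give.
- **Device use that follows allocation.** The trial is open-label and the footnote is permissive, so a reader might suspect it. The footnote, however, contrasts centres, with equipment lent to the site, and centre is a minimisation variable. A source that is constant within centre is roughly balanced between arms and costs comparability and precision. The protocol does not state that it is constant, which is worth fixing, but selective use is not shown.
- **Distorted hypotension and hypertension rates.** Nothing says that ambulatory readings feed the safety outcomes. Section 7.1.1 relies on investigator-verified measurement for hypertension and on pressor use for hypotension.

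Dropping ambulatory data from the comparison between arms would be a trade-off, since it discards the denser measurement. It is not needed to meet this point.

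**Conclusion.** The point holds in a limited form. No blood pressure or heart rate is scheduled before randomisation for any of the 260 planned patients, although the tertiary outcome is expressed as change. A change taken from the day-of-surgery value would lose whatever effect is already present, and the result could be attenuated or reversed. The 2, −4 and −8 mmHg results rest entirely on assumed effects. A comparison of perioperative levels between arms remains unbiased. It forgoes a variance reduction of 9% to 49% for assumed correlations of 0.3 to 0.7.

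The variation in source by site is a matter of comparability and precision, provided the method is constant within each centre.

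Section 5.8 describes the mechanistic work, blood pressure included, as tertiary and exploratory. The primary troponin outcome and the sample size are unaffected. This is an inexpensive improvement and does not threaten the trial's main conclusion.

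**What to change.** - **Schedule (5.6).** Add blood pressure and heart rate to the screening column, taken from the preoperative record already reviewed at that visit and dated before randomisation.
- **Outcome (2.1) and analysis.** State that perioperative values will be compared between arms with adjustment for the screening value, and that the day-of-surgery value is an outcome time point and not a baseline.
- **Source (schedule footnote).** Fix the source, ambulatory device or clinical notes, within each centre before any patient there is allocated. Account for centre in the analysis, as section 9.1 already does for the primary outcome.

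**Cost.** Two more CRF fields and a few lines of wording, with no extra visit and no change to treatment. The drawback is that a clinic reading is noisier than a standardised one and comes from a different setting, possibly some weeks earlier. That lowers its correlation with the later values and so the gain in precision. Unlike the day-of-surgery value, it cannot remove part of the treatment effect.

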5.7 Follow-up procedures

Participants will be followed up on days 1, 2, and 3 (if the patient remains in hospital) after surgery. The end of the study is defined as the point when the last patient has completed 30-day follow-up. The follow-up will be completed over the telephone and therefore the paper CRF will be the source data for any patient-reported outcomes during this period. To minimise bias, follow-up data will be collected by a study team member who is blinded to the treatment group allocation. Similarly, investigators will review a participant's medical record (paper or

[†] within 4 weeks prior to surgery

s At some centres heart rate may be measured with a Holter monitor and blood pressure cuff to collect ambulatory blood pressure (ABP) and in other sites the data will be obtained from the clinical notes. The Holter monitor and BP cuff will be loaned to the site by the Sponsor.

electronic) after surgery, unaware of the primary outcome result (which is measured after the end of the trial).

5.8 Laboratory assessments

Troponin-T (Elecsys, Roche Diagnostics) will be measured ≥ 48 hours before surgery (provided the patient is in hospital), on the day of surgery before induction of anesthesia and days 1 (± 6 hrs) and 2 (± 6 hrs) after surgery by The Doctors Laboratory, but the results will not be made available to the study team until the last study participant sample has been collected. Non-study clinicians and patients will remain blinded to the Troponin-T results throughout the study. Mechanistic studies for tertiary exploratory outcomes requiring assays of immune, neurohormonal function, electrocardiograms (ECG) and BP will be undertaken in laboratories based within Translational Medicine and Therapeutics, William Harvey Research Institute, Queen Mary University of London.

5.9 End of study definition

The end of the study is defined as the point when the last patient has completed their 30-day follow-up.

5.10 Procedures for un-blinding

Only the primary outcome of the study is blinded; therefore, treatment allocation is not blinded so no un-blinding procedures are required.

5.11 Subject withdrawal

All study participants are free to withdraw from the study at any time. All randomised patients will be included in the final analysis on an intention to treat basis, unless a participant specifically asks for their data not to be included.

5.12 Data collection and follow-up for withdrawn subjects

Patients that withdraw consent or drop out before randomisation will be replaced. The withdrawal will be documented in the CRF and medical records and although participants are not obliged to give the reason for withdrawing their consent, we will attempt to ascertain trends if possible relating to trial procedures, in case this results in a protocol amendment.

SPACE Protocol v8.0 28.01.2022 Page **21** of **42**

6 LABORATORIES

6.1 Central/ local laboratories

Troponin-T (Elecsys, Roche Diagnostics) will be measured from samples by The Doctors Laboratories ([name]) at the end of the trial when all patient samples have been collected. Tertiary outcome measures and mechanistic studies requiring laboratory assays for immune, neurohormonal, ECG and BP function will be undertaken in laboratories based within Translational Medicine and Therapeutics, William Harvey Research Institute, Queen Mary University London. The blood samples taken at each time points will be centrifuged by the site and separated into four plasma and two serum cryotubes which will then be used for all required analyses.

6.2 Sample collection/ labelling/ logging

A blood sample of approximately 14ml should be collected into a serum separator tube and two EDTA tubes at each time point. All blood samples will be pseudo-anonymised. Samples collected at each NHS Site will be labelled with the corresponding SPACE trial ID and transferred to William Harvey Research Institute (WHRI). At the end of the study the samples will be transferred from WHRI to The Doctors Laboratory for analysis. All samples will be logged with regards to the date sent to the laboratory and the temperature/conditions at which it was sent to ensure the integrity and viability are not compromised. The full sample, collection, labelling, logging and transfer procedure will be documented in the study laboratory manual.

6.3 Sample receipt/ chain of custody/ accountability

Handling of the samples upon arrival at the laboratory will be documented. Upon receipt of the samples, the laboratory will ensure that the physical integrity of these samples have not been compromised in transit. If compromise has occurred, the study team, as well as the Sponsor, will be informed of this. Upon receipt of samples, laboratory staff will ensure that all samples are accounted for as per the labelling. All samples received will be logged in a sample log.

6.4 Sample analysis procedures

For high-sensitivity troponin analysis methodology, a standard measurement protocol will be undertaken.

SPACE Protocol v8.0 28.01.2022 Page **22** of **42**

6.5 Sample storage procedures

For the purposes of tertiary and exploratory outcome studies, leukocyte samples will be stored at -80°C (unless they are tested immediately) in a dedicated research sample freezer based within Translational Medicine and Therapeutics, William Harvey Research Institute, [name].

6.6 Data recording/reporting

All troponin-T data will be measured by The Doctors Laboratory and shared by secure electronic communication after the last patient sample has been analysed.

7 PHARMACOVIGILANCE

7.1 General definitions

7.1.1 Adverse Event

An Adverse Event (AE) is any untoward medical occurrence in a subject to whom a medicinal product has been administered, including occurrences which are not necessarily caused by or related to that product. An AE can therefore be any unfavourable and unintended sign (including an abnormal laboratory finding), symptom or disease temporarily associated with the use of an IMP, whether or not related to the IMP. Only cardiovascular events or events possibly related to the SPACE procedures will be recorded as AEs and assessed accordingly.

AEs that may be expected from acute perioperative discontinuation of ACE-I or ARB (or combination of both) are listed below. Cardiovascular events such as myocardial infarction (MI), stroke and heart failure could potentially be expected from ACE-I and/or ARB withdrawal but may equally be expected from undergoing major surgery in higher-risk patients who require ACE-I and/or ARB therapy. Note that each of these events are frequently observed in higher-risk surgical patients in normal practice, so also serve as secondary outcome measures for postoperative morbidity, as applicable:

- Systolic BP>180mmHg from randomisation until 48 hours after surgery (as verified on measurement by study investigators)
- 2. Diastolic BP> 100mmHg from randomisation until 48 hours after surgery (as verified on measurement by study investigators)
- Hypotension requiring pressor via central venous access from randomisation until 48 hours after surgery

SPACE Protocol v8.0 28.01.2022 Page **23** of **42**

4. Acute kidney injury, in the absence of haemorrhage/sepsis (KDIGO grades 1-4) within 30 days after surgery.

7.1.2 Adverse Reaction

An AR is any untoward and unintended response in a subject exposed to an IMP, which is related to any dose administered to that subject. All adverse events judged by either the reporting investigator or the Sponsor as having a reasonable causal relationship to a medicinal product qualify as AR. The expression of a reasonable causal relationship means to convey in general that there is evidence or argument to suggest a causal relationship.

7.1.3 Serious Adverse Event or Serious Adverse Reaction

Only cardiovascular events or events possibly related to the SPACE procedures will be assessed for seriousness and reported where appropriate.

An SAE fulfils at least one of the following criteria:

- Is fatal results in death
- Is life-threatening
- Requires in-patient hospitalisation or prolongation of existing hospitalisation
- Results in persistent or significant disability/incapacity
- Is a congenital anomaly/birth defect
- Other important medical event

For the purposes of this study, it is up to the PI or a medically qualified delegate to decide whether the event caused the hospital stay to be prolonged. It is perfectly reasonable that patients have prolonged hospital stay due to other complications not related to the trial procedures.

A SAR is an AR that is classed as serious and which is consistent with the information about the medicinal product as set out in the Summary of Product Characteristics (SmPC) for that product.

